EVALUATION OF THE EFFECTIVENESS AND SAFETY OF ADDING IVERMECTIN TO TREATMENT IN SEVERE COVID-19 PATIENTS

Date: 04.05.2020 Version: 4

STUDY PROTOCOL

Introduction and Aim

Since the first case was reported in Wuhan, China in December 2019, the SARS CoV-2-induced COVID19 epidemic, which has surrounded the whole world with great speed, still continues its effect as a pandemic. According to the first reports, SARS CoV-2, which was reported to originate from the live animal market in Wuhan and has been associated with two bat corona viruses so far, has also gained the ability to be transmitted from person to person and spread all over the world. SARS CoV-2 is an enveloped, single-stranded betacoronavirus. The virus is mainly found in the respiratory secretions of patients and it is transmitted to susceptible people by droplets as a result of the spillage of these secretions into the environment. However, to date, it has been shown that the virus is also found in the gastrointestinal canal, feces and urine, and it has been reported that it is necessary to investigate whether it is transmitted by these means (1,2).

In a meta-analysis that evaluated nine studies and included a total of 50,404 patients, the main symptoms seen in COVID19 were reported as high fever, cough, myalgia and fatigue. In the same publication, a severe picture with acute respiratory failure is defined in 14.8% of the patients, and the average mortality is reported as 4.8% (3). In the diagnosis of the disease, lung tomography findings, which are compatible with the clinic, are particularly important (4).

The gold standard for microbiological diagnosis of the disease is to search for virus RNA in respiratory tract samples by real-time PCR. However, these tests are likely to give false negative results. In this case, radiological findings and some hematological parameters are used for diagnosis. It has been reported that most of the patients have lymphopenia, high CRP and d-dimer levels, and procalcitonin levels are close to normal. For faster diagnosis, rapid diagnostic tests have been developed to detect IgM / IgG type antibodies in blood samples of patients, and there are studies conducted to determine the sensitivity and specificity of these tests (1,3).

There is no drug with proven efficacy in the treatment of the disease. Ribavirin, hydroxychloroquine, lopinavir-ritonavir, remdesivir, favipiravir, azithromycin are among the drugs being tried. In patients with severe prognosis and with septic shock, cytokine antagonists such as corticosteroids, tocilizumab, and plasma treatments obtained in recovered patients are tried (5,6).

Ivermectin, which is an antiparasitic drug effective against endo and ecto parasites in the structure of 22,23 dihydroavermectin B1, which is produced semi-synthetically from the avermectin family, has been approved by the FDA for oral use in humans, it is a highly effective drug for ascariasis, cutaneous larval migrans, strongiloidosis, onchocerciasis, and scabies (7).

In addition to its antiparasitic activity, ivermectin has been shown in in vitro studies in recent years that it has antiviral efficacy against many viruses such as human immunodeficiency virus (HIV-1), dengue virus and western nile virus. In a phase 3 study between 2014 and 2017 in people with Deng virus infection in Thailand, it was reported that orally once a day was used and it was safe, and it did not provide clinical improvement, although a significant decrease was observed in the serum viral NS1 protein level (8, 9).

The most common side effects during ivermectin treatment; fever, headache, dizziness, itching and rash. Rarely, neurological side effects such as encephalopathy, confusion and coma have been reported during the use of ivermectin in the treatment of onchoceriosis. These side effects have been shown in animal and human studies to be related to the mdr-1 gene mutation. It has been shown that in persons carrying the SNP (single nucleotide polymorphisms) mutation in the mdr-1 / abcb1 gene encoding P-glycoprotein, this gene expression decreases and ivermectin passes to the central nervous system and accumulates and leads to encephalopathy.

In addition, it has been reported that haplotypes and mutations in the CYP3A4 Gene that give and lose function cause toxic effects or drug dosing by changing the metabolic rate of ivermectin.

In a recently published in vitro study from Australia, the efficacy of ivermectin used as an antiparasitic agent on SARS-CoV-2 was evaluated and Vero/hSLAM cells were infected with this virus in vitro and exposed to ivermectin, after 48 hours there was a 99.8% reduction in viral load. Based on these studies, it can be thought that ivermectin, which has also been shown to have antiviral efficacy in different studies, may also be effective in COVID19 patients (8).

In this study, it is aimed to evaluate the effect of ivermectin addition to the "Hydroxychloroquine ± Favipiravir ± Azithromycin" combination therapy, which is the reference treatment recommended in the "Covid19 Guideline" prepared by the Ministry of Health, on clinical response in patients with severe COVID19 pneumonia and to investigate the safety of ivermectin use in these patients (10).

Material and Method

The study will be conducted as a prospective, randomized, controlled, single-blind Phase 3 study. Patients with severe COVID19 disease who were hospitalized in Afyonkarahisar Health Sciences University, Health Sciences University Istanbul Sultan Abdülhamid Han Training and Research Hospital, Ankara City Hospital and Health Sciences University Ankara Gülhane Training and Research Hospital COVID19 service and intensive care units will be included in the study.

There will be two patient groups in the study, the study arm and the control arm. A total of 60 patients, including 30 in both arms, are planned to be included in the study.

Patient Selection and Inclusion Criteria

Patients who were hospitalized with a pre-diagnosis of *severe COVID-19 pneumonia and thereafter diagnosis of COVID-19 was also confirmed microbiologically with PCR positivity in respiratory tract samples were included into the study (13). They were randomized to the study and control group, respectively.

- * Patients with at least one of the criteria below were accepted as patients with severe COVID-19 pneumonia;
- a. Presence of tachypnea ≥30/minute, SpO2 level <90% in room air, PaO2/FiO2 <300 in oxygen receiving patient
- b. Presence of specific radiological finding for Covid-19 in lung tomography (bilateral lobular, peripherally located, diffuse patchy ground glass opacities)
- c. Mechanical ventilation requirement
- d. Acute organ dysfunction findings; patients with SOFA (sepsis-related organ failure assessment) score> 2

THE SEQUENTIAL ORGAN FAILURE ASSESSMENT (SOFA) SCORE

0	1	2	3	4
> 400	<400	<300	<200 (26.7)	<100 (13.3)
(53.3)	(53.3)	(40)	with respiratory support	with respirator support
≥150	<150	<100	<50	<20
<1.2	1.2-1.9	2.0-5.9	6.0-11.9	>12.0
(20)	(20-32)	(33-101)	(102-204)	(204)
MAP	MAP	Dopamine <5	Dopamine 5.1 - 15 or	Dopamine >15
≥70mmHg	<70mmHg	or Dobutamine	Epinephrine ≤ 0.1 or	or Epinephrine
		(any dose)	Norepinephrine ≤ 0.1	>0.1 or Norep nephrine >0.1
15	13-14	10-12	6-9	<6
<1.2 (110)	1.2 -1.9	2.0 - 3.4 (171-	3.5 - 4.9	> 5.0 (440)
	(110-170)	299)	(300 -440)	<200
	(110 110)		<500	1200
	≥400 (53.3) ≥150 <1.2 (20) MAP ≥70mmHg	≥400 <400 (53.3) (53.3) ≥150 <150 <1.2 1.2-1.9 (20) (20-32) MAP MAP ≥70mmHg <70mmHg	≥400	≥400

Mutations in the mdr1 / abcab1 gene and the CYP3A4 gene will be investigated in patients who meet any of the above criteria and are > 18 years of age and enrolled in the study group by randomization. Patients with mutations will not be included in the study.

Exclusion Criteria

Patients with the following characteristics were excluded from the study.

- 1. Pediatric patients; <18 years of old
- 2. Patients with chronic liver or kidney disease
- 3.Pregnant women
- 4. Patients with known ivermectin allergy

Genetic study

In the patients included in the study group, the mutation in 29 pairs of primers and the haplotypes and mutations of the CYP3A4 gene will be investigated by performing sequence analysis in the mdr1 / abcab1 gene with the Sanger method.

Design of Primers

"PRIMER © – Primer Designer v.2.0 (Scientific & Educational Software)" software will be used in primer design for mutation research. Primers will be synthesized by Metabion International AG. Sequence analysis plan and primer design will be made, including the coding regions of these genes, exon-intron junction regions.

Sanger Sequence Analysis

DNA fragments for all patients will be sequenced with the ABI 3130 sequence analyzer after amplification using polymerase chain reaction (PCR) followed by bidirectional fluorescent markers using BigDye chemistry (Life Technologies, Carlsbad, CA, USA). The sequences will be read with the Seqscape program. Variants obtained here will be analyzed according to ACMG criteria and variants will be classified. In the analysis of variants, data will also be evaluated using relevant databases to identify known haplotypes.

Treatment and patient follow-up

The following reference treatment recommended by the Ministry of Health will be applied to all patients in the control and study groups;

- 1. Hydroxychloroquine (2x400mg loading dose followed by 2x200mg, po, 5 days)
- 2. Favipiravir (2x1600mg loading followed by 2x600mg, po, maintenance dose for a total of 5 days)
- 3.Azithromycin (500mg first day followed by 250mg / day 4 days, po, 5 days total)

In addition to the reference therapy, ivermectin at a dose of 200 mcg / kg / day (9 mg between 36-50 kg, 12 mg between 51-65 kg, 15 mg between 66-79 kg,> 80 kg 200mcg / kg) It will be applied for five days in the form of a solution prepared for enteral use (Ivermectin 5mg/5ml solution was manufactured by Neutec Pharmaceutical-Turkey, under GMP conditions).

Patients in the control arm will be given reference treatment with the other 3 drugs without giving ivermectin.

The drug whose effectiveness will be evaluated in the study is ivermectin. Ivermectin is an FDA-approved antiparasitic drug. Approved adult dose in parasitic infections is reported as 200mcg / kg / day (11). Although ivermectin has been shown to be effective in SARS CoV-2 in vitro, there is no randomized prospective controlled study showing that it is effective in COVID19 patients. In a very recent study that is still in press, it has been reported that it significantly reduces mortality in COVID19 patients, and in this study, no information is given about the duration and dosage of use (12).

In a study conducted in Thailand on the use of ivermectin in dengue fever infection, it was reported that it was used at doses of 200mcg / kg / day and 400mcg / kg / day (13).

Ivermectin antiparasitically as a single daily or multi-dose intermittent sequential; In dengue fever infection, considering the use of 200 or 400 mcg / kg / day as an antiviral for 3 days, it is seen that the total dose given in antiviral treatment reaches up to 1200 mcg / kg / day (14,15,16). Based on all these studies, we planned to use ivermectin at a dose of 200 mcg / kg / day, which is approved by the FDA, in our study. Definitive recommendations for treating COVID19 disease Although not, the duration of treatment with antiviral drugs is recommended as 5 days in the guide prepared by the Scientific Committee of the Ministry of Health. Considering that the average duration of symptoms in patients is 5-7, the duration of ivermectin treatment was planned as 5 days in our study, and it was planned to reach a total dose of 1000 mcg / kg / day, close to the total dose used in viral infections in the literature. The treatment can be terminated in less than 5 days if the patients reach the treatment early or if there are side or toxic effects.

Study Design

In all patients included in the study; demographic data, comorbid conditions, admission symptoms, complete blood count and biochemical blood examinations at the time of admission, initial SARSCoV-2 PCR results and thoracic tomography findings at presentation will be recorded.

During the study; respiratory findings and laboratory parameters of the patients will be recorded on the 1st, 3rd and 5th days of the treatment and on the 1st, 3rd and 5th days after the treatment, during the follow-up period. Side effects observed during the treatment in all patients also will be recorded.

Primary and secondary endpoints for efficacy and safety assessment in the study will be determined as follows:

Primary endpoint: Clinical responses and drug side effects obtained in patients on the 5th day, at the end of the ivermectin treatment will be evaluated. Extubation in mechanically ventilated patients, respiratory rate <26, SpO2 level in room air > 90%, PaO2 / FiO2> 300 in patients receiving oxygen, presence of at least two of the 2-point reduction criteria in SOFA score will be evaluated as "*clinical response*".

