Date: 04.05.2020 Version: 3

STATISTICAL ANALYSIS PLAN

Study name: Evaluation Of The Effectiveness And Safety Of Adding Ivermectin to

Treatment in Severe COVID-19 Patients

Study protocol cod: IVMC_03

Ethics committee approval number and date: 139/03.04.2020

Coordinator researcher: [name]. [name]

STATISTICAL ANALYSIS PLAN

Convenience Sampling method will be used in the study. Unilateral blinding will be made in determining which of the study and control groups participating patients will be included in the study, those with an odd number will be included in the study group, and those with an even number will be included in the control group.

In determining the sample size, it was planned to include 30 individuals in each group based on the number of available kits. In this case, the values of 0.05 for Type I Error Rate, 0.67 for Effect Size and 0.80 for Power were reached.

The Chi-Square test will be used in the evaluation of categorical data, the Wilcoxon test for in-group comparisons, and the Mann-Whitney U test for intergroup comparisons. For statistical significance, the value of p=0.05 will be taken into account and the analyzes will be carried out in the SPSS 20.0 package program.

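### On the more natural reading, mutation carriers are removed after allocation from the ivermectin arm only, and no analysis population says how they are counted

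*Protocol*

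**What the plan says.** Three sentences in the protocol say who is sequenced.

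- **Patient Selection and Inclusion Criteria, paragraph after the SOFA table.** Testing is planned in eligible adults "enrolled in the study group by randomization. Patients with mutations will not be included in the study". The exclusion follows directly on the sentence about the study group, but itself names no arm.
- **Genetic study.** "In the patients included in the study group, the mutation in 29 pairs of primers" are to be examined, along with CYP3A4. This again means the study group.
- **Sanger Sequence Analysis.** "DNA fragments for all patients will be sequenced with the ABI 3130 sequence analyzer". This may mean both arms, or only all patients who are sequenced.

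Mutation status is not among the four numbered exclusion criteria. No passage provides for testing before allocation, for removing control carriers or for replacing removed patients. On what counts as a mutation, the text says only: "Variants obtained here will be analyzed according to ACMG criteria and variants will be classified".

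In the SAP, allocation is by number: "those with an odd number will be included in the study group", even numbers going to control. On size, "it was planned to include 30 individuals in each group based on the number of available kits". On the binary comparison, "The Chi-Square test will be used in the evaluation of categorical data". Neither document names an analysis population.

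The reason for testing is in the protocol's Introduction, which describes rare neurological effects of ivermectin: "These side effects have been shown in animal and human studies to be related to the mdr-1 gene mutation". It also links CYP3A4 variants to toxicity. Drug side effects are part of the day-5 primary endpoint, and the Study Design section says that side effects during treatment are recorded in all patients.

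**The concern.** Allocation makes the arms comparable only if everyone allocated is analysed, or if the same exclusion applies to both arms. Here a patient characteristic is found after allocation and, on the more natural reading, used to remove patients from one arm. The ivermectin arm would hold non-carriers only, while the control arm would hold carriers and non-carriers.

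Two results are exposed.

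- **Efficacy.** If carriers respond differently under reference treatment, the arms differ even when ivermectin does nothing.
- **Safety.** The patients removed are those whom the protocol itself expects to be at higher risk from ivermectin. The observed side-effect rate would describe screened non-carriers, and the protocol does not state that limit. It is also not stated whether sequencing results arrive before the first dose. If they do not, it is open whether side effects in a carrier who was dosed and then removed enter the analysis.

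**Working it through.** **The plan's own figure.** The SAP reports power 0.80 for 30 per group, effect size 0.67 and alpha 0.05. Using t-test power with the sample size multiplied by 3/π to approximate the Mann-Whitney test, I get 0.805 one-sided and 0.702 two-sided. The stated figure therefore reproduces as a one-sided test; the SAP does not give sidedness. The point here does not depend on it.

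**Inputs.** From the documents: 30 per arm, alpha 0.05, chi-square test. Assumed, because the documents give no figure: carrier share m = 5, 10, 20 or 30%; response gap g between non-carriers and carriers of 10 or 20 points under reference treatment; 50% response in non-carriers.

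**Efficacy bias with no drug effect.** The ivermectin arm responds at p (non-carriers). The control arm responds at (1 − m)p + m(p − g) = p − mg. The spurious difference is m × g:

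| m | g = 10 points | g = 20 points |
|---|---|---|
| 5% | 0.5 | 1 |
| 10% | 1 | 2 |
| 20% | 2 | 4 |
| 30% | 3 | 6 |

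It favours ivermectin if carriers do worse, favours control if they do better, and is 0 if genotype is unrelated to outcome.

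**Type I error.** Exact binomial enumeration of the uncorrected chi-square test, two-sided 0.05, 30 v 30 analysed, ivermectin arm at 50%, carriers doing worse:

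| Control rate | Bias (points) | Favouring ivermectin | Favouring control | Total |
|---|---|---|---|---|
| 50% | 0 | 2.6% | 2.6% | 5.2% |
| 49% | 1 | 3.1% | 2.2% | 5.3% |
| 48% | 2 | 3.7% | 1.8% | 5.5% |
| 46% | 4 | 5.1% | 1.2% | 6.3% |
| 44% | 6 | 6.9% | 0.8% | 7.7% |

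If carriers do better, the two one-sided columns swap.

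**Could the control arm settle whether genotype matters?** If controls are sequenced and 3, 6 or 9 of 30 are carriers, the standard error of the carrier v non-carrier difference at 50% response is √(0.25/3 + 0.25/27) = 30 points, √(0.25/6 + 0.25/24) = 23 points, or √(0.25/9 + 0.25/21) = 20 points. That is too imprecise to detect a 20-point gap.

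**Safety.** If carriers on ivermectin had an assumed 20 points more side effects, screening them out would lower the observed rate by m × 20 = 1, 2, 4 or 6 points relative to unscreened patients.

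**Power if carriers are undosed but analysed as allocated.** With ivermectin response P, control response 50% and undosed carriers responding at 50%, the ivermectin arm responds at P − m(P − 0.50). Two assumed values of P are used. The first is 70%. The second reads the SAP's 0.67 as Cohen's h from 50% (the SAP does not name the metric): P = sin²[(2·arcsin√0.5 + 0.67)/2] = 81%. The same exact test gives the power to show benefit:

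| m | 70% v 50%, as allocated | 70% v 50%, carriers removed | 81% v 50%, as allocated | 81% v 50%, carriers removed |
|---|---|---|---|---|
| 0 | 35% | 35% | 73% | 73% |
| 5% | 32% | 35% | 68% | 73% |
| 10% | 29% | 34% | 62% | 71% |
| 20% | 24% | 32% | 51% | 69% |
| 30% | 19% | 31% | 41% | 66% |

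The removed columns assume no replacement, leaving 28, 27, 24 or 21 v 30.

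**The case against.** **One-arm removal is an inference.** The exclusion sentence names no arm, and the sentence about sequencing all patients would fit a study-wide rule. This stands, and it limits the severity. If one rule for both arms was intended, the one-arm imbalance goes, but the timing of testing and the counting of removed patients stay open. As written, no sentence removes a control carrier.

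**No efficacy bias is shown.** Genotype is fixed before allocation, so removal by genotype does not depend on treatment or outcome. Bias also requires genotype to predict outcome under reference treatment, and no passage says it does. At 10% carriers and a 20-point gap, total error moves only from 5.2% to 5.5%. This stands too. A reader might infer that the design favours ivermectin; the documents support neither a direction nor a size.

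**The safety point is mainly about whom the result applies to.** In screened patients the side-effect rate is not biased for screened patients. This stands. A reader might also infer that carriers' side effects would go unrecorded, but the Study Design section records them in all patients. What is open is whether those of a carrier removed after dosing are analysed.

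**As-allocated analysis can cost a good deal of power.** This stands: up to 32 points (73% to 41%) on one reading of the planned effect. It is why genotyping both arms before allocation is an equally acceptable remedy.

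A reader might add that odd/even allocation makes this worse. That is a separate matter: removal by genotype does not make allocation more predictable.

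**Conclusion.** The point holds as a gap in design and analysis, not as a demonstrated bias. Two of the three sentences place testing after allocation and in the ivermectin arm, the exclusion follows the first of them, and nothing in either document says how removed patients are counted. Followed that way, the trial compares screened ivermectin patients with unscreened controls.

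The numerical consequences rest wholly on assumed carrier shares and gaps, and on 50% response. Within the ranges tried the inflation of error is modest. The safety conclusion would be limited to screened non-carriers, and the protocol should say so because side effects are part of its primary endpoint.

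This should be fixed, but it does not rank as a must-fix: one-arm removal is the more natural reading rather than an explicit rule, and the documents give no evidence that genotype affects COVID-19 outcome.

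**What to change.** 1. **Reconcile the three sequencing sentences.** State which arms are tested, and whether the result is due before or after allocation and the first dose. In the same amendment, define which variant classes count as a mutation.
2. **Choose one of two equally acceptable routes and write it into the SAP.**
   - *Testing stays after allocation:* keep carriers in follow-up, collect their outcomes at day 5 and at day 5 after treatment, and make the primary efficacy analysis all allocated patients in their allocated arm. Report the carrier-excluded analysis as a labelled sensitivity analysis. Whether carriers receive ivermectin is a clinical decision for the sponsor.
   - *Testing moves before allocation:* apply one eligibility rule to both arms, if sequencing capacity and turnaround allow.
3. **Safety.** Analyse side effects by treatment received, counting any carrier with at least one dose. If carriers are not dosed, limit the safety conclusion to screened non-carriers.

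**Cost.** A protocol amendment and one SAP paragraph. The first route adds follow-up of 30m, or about 2, 3, 6 or 9 carriers at 5, 10, 20 or 30%; if carriers are replaced until 30 non-carriers remain, it is 30/(1 − m) − 30, or about 2, 3, 8 or 13. It also brings the dilution shown in the power table, and because the sample size was set by available kits, enrolling more patients may not recover the loss. The second route avoids dilution but needs more sequencing and a wait before allocation.

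### The safety aim covers severe COVID-19 patients, but carriers of toxicity-linked variants are removed after allocation to ivermectin and no safety set keeps any doses or side effects they had.

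*Protocol*

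**What the plan says.** **Aim.** The aim paragraph (Protocol, Introduction and Aim) sets out to evaluate the effect of adding ivermectin "on clinical response in patients with severe COVID19 pneumonia and to investigate the safety of ivermectin use in these patients". It sets no genotype limit. Under Study Design, side effects are part of both the primary and the secondary endpoint.

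**Risk factor.** The same introduction says of mdr-1/abcb1 carriers that "this gene expression decreases and ivermectin passes to the central nervous system and accumulates and leads to encephalopathy". It is less specific on the second gene, saying that "haplotypes and mutations in the CYP3A4 Gene that give and lose function cause toxic effects or drug dosing" through a changed metabolic rate.

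**Screen.** After the SOFA table, under Patient Selection and Inclusion Criteria: "Mutations in the mdr1 / abcab1 gene and the CYP3A4 gene will be investigated in patients who meet any of the above criteria", are adults and are "enrolled in the study group by randomization". The next sentence reads "Patients with mutations will not be included in the study". The Genetic study section also confines the work to the study group, but Sanger Sequence Analysis says "DNA fragments for all patients will be sequenced with the ABI 3130 sequence analyzer".

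**What is absent.** Genotype is not among the four numbered exclusion criteria. The SAP mentions neither the genetic exclusion nor a safety population.

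**The concern.** A safety result describes the patients in whom side effects are counted. Here patients are removed on a factor that the protocol itself connects with toxicity, and as written the removal follows allocation to the drug under study. Two things are at stake.

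- **Scope.** For the toxicity tied to these genes, the trial observes only patients cleared by sequencing, while the aim is worded for severe COVID-19 patients in general. This limit would remain even if both arms were screened alike.
- **Completeness.** If a carrier receives ivermectin before the sequencing result is known and is then treated as not included, that exposure and any reaction to it may appear nowhere. Such a patient is one whom the protocol considers to be at higher risk.

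**Working it through.** The SAP's one computed result, power of 0.80 with 30 per arm, does not bear on this point. The check is a reading of the passages against each other, plus one calculation for scale.

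1. **Question against population.** The aim names patients with severe COVID-19 pneumonia. The population left after the selection section is patients with severe COVID-19 pneumonia and, at least in the ivermectin arm, no mutation found in either gene. The two differ by exactly the variants that the introduction links to toxicity.

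2. **Timing.** The text sequences patients who are already in the study group. It does not say whether the result is awaited before the first dose.
   - If it is awaited, no carrier is exposed, no event is lost, and only the limit on scope remains.
   - If it is not awaited, carriers may have been dosed by the time they are removed.

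3. **What happens to a dosed carrier.** Study Design has side effects recorded in every patient during treatment. It does not say whether a patient who is not included because of a mutation still counts. The SAP names the tests, the allocation rule and the sample size, but no analysis set, so nothing obliges the analyst to keep that patient.

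4. **Which variants exclude.** Variants are to be classified by ACMG criteria, but no class is named as the ground for exclusion. The screened population is therefore not exactly defined.

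5. **Who is sequenced.** Two passages say the study group and one says all patients. On the first reading, controls may include carriers, and the label mutation-free fits the ivermectin arm only.

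6. **Scale.** Inputs: 30 patients per arm (Protocol, Material and Method) and a carrier proportion c, which the documents do not give. I assume c from 0.05 to 0.30.
   - Expected number removed from 30 allocated = 30 × c: 30 × 0.05 = 1.5 and 30 × 0.30 = 9.
   - Number to allocate to leave 30 = 30 / (1 − c), rounded up: 30 / 0.95 = 31.6, so 32; 30 / 0.70 = 42.9, so 43.

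   The documents do not say whether 30 is counted before or after removal. The number of carriers dosed before removal lies between none and all of those removed.

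**The case against.** The strongest reply is that this is ordinary eligibility. The restriction is disclosed in the selection section and the introduction gives its reason. Eligibility criteria normally define the population to which an aim applies. The aim does not repeat the exclusions for liver or kidney disease, pregnancy or allergy either. All of that stands, and excluding patients thought to be at risk is legitimate. What it does not answer is the timing: the text places this screen after allocation to ivermectin, and no rule covers a carrier who has already been dosed.

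A reader might infer three stronger things, none of which the documents support.

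- **That the plan claims safety for all severe patients.** It does not. The aim is to investigate, and no conclusion is written in either document.
- **That the trial cannot answer its safety question.** This goes too far. The introduction does not attribute the common side effects (rash, itching, dizziness, headache, fever) to genotype, so it gives no reason to think the screen changes their rate. It also calls the serious neurological effects rare and places those reports in onchocerciasis treatment.
- **That the understatement of risk can be given in percentage points.** The documents supply neither carrier frequency nor toxicity rates by genotype, so any such figure would be set by the assumptions chosen.

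**Conclusion.** The point holds in limited form. For mutation-related toxicity, the safety result applies to patients who passed the sequencing screen, and the documents do not state that limit beside the aim or in the SAP. Doses and side effects in carriers before removal could also be lost. That is a possibility left open by the text, not something the documents say will happen, and it depends on whether results precede dosing.

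No effect on a side-effect rate can be computed. The count of 1.5 to 9 removed out of 30 rests wholly on the assumed carrier range and shows only that the number need not be negligible in an arm of this size. The matter should be corrected because it is cheap and changes what the trial can conclude. It does not invalidate the study of common side effects.

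**What to change.** 1. **SAP, safety set.** Define it as every patient who received any dose of ivermectin, including those later removed for a mutation. Report the removed patients' doses and events, and list them separately so that they are visible.
2. **SAP, screening table.** Report by arm the number sequenced, and the number and class of the variants that led to exclusion. If controls are not sequenced, the table should say so.
3. **Aim and planned conclusion.** Limit the safety conclusion to patients who passed the sequencing screen. A few partly exposed carriers in the safety set would not support a conclusion about carriers.
4. **Protocol, consistency.** Reconcile the study-group and all-patients statements on who is sequenced. Name the variant classes that exclude, add the genetic exclusion to the numbered list, and state whether sequencing results are available before dosing. I take no view on what the clinical rule should be.

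The cost is a narrower claim and one additional table, largely from data that the sequencing already produces. If any carrier is dosed before removal, side-effect recording for that patient must also continue after removal.
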